3.4.4 Handling of Missing Data and Outliers

Generally, no replacement will be done for Safety Missing Data and Outliers. For immunogenicity, no imputation of missing values and no search for outliers will be performed.

3.4.4.1 Safety

3.4.5.1.1 Immediate

For unsolicited systemic AEs, a missing response to the "Immediate" field is assumed to have occurred after the 30-minute surveillance period and will not be imputed.

3.4.5.1.2 Causal Relationship

By convention, all events reported at the injection site (either solicited or unsolicited) will be considered as related to the administered product and then referred to as reactions. In a same way, all solicited systemic events pre-listed in the CRF are also considered as related to vaccination and will be considered as reactions.

- For unsolicited systemic AE, missing relationship will be considered as related to study vaccine at the time of analysis.
- The missing relationship to study procedures for SAEs will not be imputed.

3.4.5.1.3 Intensity

For solicited reactions, missing intensities will be handled as described in Section 4.2.1.1.1. For unsolicited AEs, missing intensities will remain missing and will not be imputed.

3.4.5.1.4 Start Date and End Date

Missing or partially missing start dates or end dates for unsolicited AEs (including SAEs) will remain missing and not be imputed. If the start date is missing or partially missing, the time of onset will be considered to be missing. Nevertheless, unsolicited AEs with missing time of onset

will be included in analyses within or not within the defined time window (according to the Section 4.2.1.2.4), according to the last vaccination (computed according to the Section 4.2.1.2.3),. If either the start date or end date is missing or partially missing, the duration will be considered missing.

Missing or partially missing end dates for ongoing solicited AEs will remain missing and not be imputed.

3.4.5.1.5 Action Taken

Missing actions taken will remain missing and not be imputed.

3.4.4.2 Immunogenicity

No imputation of missing values and no search for outliers will be performed. LLOQ and ULOQ management will be performed as described in Section 4.2.3.1.

3.5 Interim Analysis

An interim report may be generated with hSBA analysis of all immunogenicity endpoints and safety endpoints depending on the timelines regarding the availability of the rSBA data. Final report will be generated with the analyses of rSBA immunogenicity endpoints.

This study will not include an early safety data review. No additional analyses are planned to be performed prior to the formal completion of the study.

3.6 Data Monitoring Committee (DMC)

Not applicable.

4 Complementary Information on Assessment Methods

Study assessments and procedures are detailed in Section 8 of the protocol. This section focusses on complementary/additional information not detailed in the protocol.

4.1 Complementary Information for Endpoints Assessment Methods

Not applicable.

4.2 Complementary Information on Derived Endpoints: Calculation Methods

4.2.1 Safety

4.2.1.1 Solicited Reactions

4.2.1.1.1 Daily Intensity

All daily records for solicited reactions will be derived into daily intensity according to the following classification: None, Grade 1, Grade 2, Grade 3, or Missing (Unknown).

For the derivation of daily intensities, the following sequential steps will be applied:

- 1) Solicited reactions (except Fever/Pyrexia) with CRF presence recorded as "No" and with all daily records missing (Unknown) then all daily intensities will be derived as None.
- 2) For non-measurable solicited reactions, daily intensities will correspond to daily records reported in the clinical database. For measurable solicited reactions the daily measurements reported in the clinical database will be converted based upon the intensity scales defined in the protocol; this assumes a reaction that is too large to measure (non-measurable, "NM") is Grade 3.

Note: The maximum intensity on the ongoing period is derived from the record of the maximum intensity/measurement after the end of the solicited period following the rule described above.

Table 4.1: Solicited injection site reactions: terminology, definitions, and intensity scales – Infants and toddlers aged ≤ 23 months

CRF term (MedDRA lowest level term [LLT])	Injection site tenderness	Injection site erythema	Injection site swelling
Diary card	Tenderness	Redness	Swelling
term Definition	touched or injected limb mobilized	including the approximate point of needle entry	Swelling at or near the injection site Swelling or edema is caused by a fluid infiltration in tissue or cavity and, depending on the space available for the fluid to disperse, swelling may be either soft (typically) or firm (less typical) to touch and thus can be best described by looking at the size of the swelling
Intensity			Grade 1:
scale*	when injection site is touched	≥ 25 to < 50 mm Grade 3: ≥ 50 mm	> 0 to < 25 mm Grade 2: ≥ 25 to < 50 mm Grade 3: ≥ 50 mm

^{*} For tenderness, the scale will be provided in the CRF and the intensity will be transcribed from the diary card. For other injection site reactions (erythema and swelling), the classification as Grade 1, 2, or 3 will be applied at the time of statistical analysis; the scale is provided for information purposes only. The actual size of the reaction will be reported in the CRF.

Table 4.2: Solicited systemic reactions: terminology, definitions, and intensity scales – Infants and toddlers aged \leq 23 months

CRF term	Fever	Vomiting	Crying abnormal	Drowsiness	Appetite lost	Irritability
(MedDRA						
lowest level						
term [LLT])						
Diary card	Temperature	Vomiting	Abnormal crying	Drowsiness	Loss of	Irritability
term					appetite	
Definition	Elevation of	Vomiting does not	Inconsolable crying	Reduced interest	See intensity	An excessive
	temperature to	include spitting	without a determined	in surroundings,	scale	response to stimuli:
	≥°38.0°C	up	reason	or increased		increased fussiness,
	(≥100.4°F)			sleeping		whining, and

CRF term (MedDRA lowest level term [LLT])	Fever	Vomiting	Crying abnormal	Drowsiness	Appetite lost	Irritability
						fretfulness despite attempts to comfort the infant and despite caregiver responses that would normally be soothing
Intensity scale*		1 episode per	Grade 1: CRF and DC: < 1 hour	Sleepier than	Grade 1: CRF and DC: Eating less than normal	Grade 1: CRF and DC: Easily consolable
	Grade 2: > 38.5°C to ≤ 39.5°C or > 101.3°F to ≤ 103.1°F	CRF and DC: 2– 5 episodes per	Grade 2: CRF and DC: 1– 3 hours	Grade 2: CRF and DC : Not interested in surroundings or did not wake up for a feed / meal	CRF and DC: Missed 1 or 2 feeds / meals	Grade 2: CRF and DC: Requiring increased attention
	or > 103.1°F	$CRF: \ge 6$ episodes	Grade 3: CRF and DC: > 3 hours	of the time or difficult to wake	Grade 3: CRF and DC: Refuses ≥ 3 feeds / meals or refuses most feeds / meals	Grade 3: CRF: Inconsolable DC: Inconsolable (cannot be comforted)

^{*} For all reactions (except fever), the scale will be provided in the CRF and the intensity will be transcribed from the diary card. For fever, the body temperature will be recorded, and the classification as Grade 1, 2, or 3 will be assigned at the time of the statistical analysis based on the unit used to measure the temperature and the intensity scale.

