4.2.1.1.2 Maximum Intensity

Maximum overall intensity is derived from the daily intensities computed as described in Section 4.2.1.1.1 and is calculated as the maximum of the daily intensities over the period considered.

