4.2.1.1.3 Presence

Presence is derived from the maximum overall intensity over the time period considered:

- None: No presence
- Grade 1, Grade 2, or Grade 3: Presence
- Missing or Unknown: Missing presence

Participants with at least one non-missing presence for a specific endpoint will be included in the analysis. Conversely, those without a non-missing presence will not be included in the analysis of the endpoint.

The time period is displayed as D1-D4, D5-D8, D9 and later.

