4.2.2.5 Adverse Events Leading to Study Discontinuation

This information will be summarized as collected. A flag is available in the clinical database for all AEs in order to identify AEs leading to discontinuation before the end of active phase. In general, the items that are counted are:

- Disposition table: A participant who, on the "Completion at End of Study" form question "What was the participant's status?" has "Adverse Event" checked.
- Safety overview table: A participant who has either on the "Completion at End of Study" form, question "What was the participant's status?" has "Adverse Event" checked or lists a solicited AE that has "Caused Study Termination" checked that is at least Grade 1 or an unsolicited AE that has "Caused Study Discontinuation" checked that is at least Grade 1 or missing and is within the time period indicated.
- System Organ Class (SOC)/Preferred Term (PT) table: A solicited AE that has "Caused Study Termination" checked that is at least Grade 1 or an unsolicited AE that has "Caused Study Discontinuation" checked that is at least Grade 1 or missing and is within the time period indicated.

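### For the eight non-fever solicited reactions, the SAP keeps a recorded 'No' without daily records as a non-event but lets a recorded 'Yes' without daily records drop out as missing

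*SAP*

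**What the plan says.** SAP 3.4.5.1.3 sends the reader to one place: "For solicited reactions, missing intensities will be handled as described in" section 4.2.1.1.1. That section has two steps.

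- Step 1 applies to "Solicited reactions (except Fever/Pyrexia) with CRF presence recorded as" 'No', "with all daily records missing (Unknown) then all daily intensities will be derived as None".
- Step 2 covers everything else: "For non-measurable solicited reactions, daily intensities will correspond to daily records reported in the clinical database". Measured reactions are converted from the recorded size or temperature, and one too large to measure becomes Grade 3.

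SAP 4.2.1.1.2 then defines the maximum intensity, which "is calculated as the maximum of the daily intensities over the period considered". SAP 4.2.1.1.3 derives presence from that maximum: "Missing or Unknown: Missing presence". It adds that "those without a non-missing presence will not be included in the analysis of the endpoint".

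SAP 4.2.2.5 sets the conditions for counting an event that ended participation. The solicited branch stops at Grade 1 before the text moves on to unsolicited events: "checked that is at least Grade 1 or an unsolicited AE that has". The unsolicited branch also accepts a missing grade. The safety overview and the SOC/PT table both use this pair of conditions. The disposition table and the safety overview also count a child whose completion form gives an adverse event as the reason.

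**The concern.** The safety endpoint in Protocol Table 3.1 and SAP Table 2.1 is the presence of a solicited reaction within 7 days. A CRF 'Yes' answers that question even when no grade is known. The SAP uses the CRF answer only when it is negative, so for eight of the nine solicited reactions (three at the injection site, five systemic) a recorded negative survives without daily data and a recorded positive does not.

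This differs from how the SAP treats missing information on unsolicited events: missing causality counts as related (3.4.5.1.2), a wholly missing start date counts as within 30 days (4.2.1.2.4), and a discontinuation event of missing grade counts (4.2.2.5). SAP 4.2.1.1.7 gives a reason for setting aside the investigator's ongoing flag, but no reason is given for setting aside a positive presence answer.

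At stake are the percentages of toddlers with each non-fever solicited reaction, a main output of a descriptive safety study, and whether the SOC/PT table names an ungraded solicited reaction that ended participation.

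**Working it through.** **Tracing the two answers.** Take a non-fever reaction, a CRF answer and no daily records.

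| Step | CRF 'No' | CRF 'Yes' |
|---|---|---|
| 4.2.1.1.1 step 1 | all days None | does not apply |
| 4.2.1.1.1 step 2 | not needed | daily intensity follows the daily record: Missing |
| 4.2.1.1.2 maximum | None | Missing |
| 4.2.1.1.3 presence | No | Missing |
| In the analysis? | denominator only | neither numerator nor denominator |

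The 'Yes' column follows from the absence of a rule together with 4.2.1.1.3. It is not an explicit instruction.

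**Direction.** Let c children have complete diaries, Y of them with the reaction. Let m further children have a CRF answer and no daily records, y of them 'Yes'. Write D = c + m.

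- SAP rate, non-fever: Y / (D − y)
- Rate using every recorded answer: (Y + y) / D

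The SAP rate is the lower one when Y·D < (Y + y)(D − y), which reduces to 0 < y(D − Y − y). This is true whenever y > 0 and at least one child has no reaction. With y = 0 the two rates are equal.

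**Scale from the plan.** SAP 3.2 plans about 180 children, at least 150 evaluable and about 15% drop-out. 150/0.85 = 176.5, so 177, consistent with 180; and 180 × 0.85 = 153, leaving 27. No solicited-reaction rate and no count of children without daily records appears in the documents. I therefore assume a rate of 40% (0.40 × 153 = 61 reactors among 153 complete diaries) and vary m.

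- m = 10 (4 Yes, 6 No): SAP 61/(153 + 6) = 61/159 = 38.4%. All answers (61 + 4)/(153 + 10) = 65/163 = 39.9%. Difference −1.5 points.
- m = 27 (11 Yes, 16 No): SAP 61/(153 + 16) = 61/169 = 36.1%. All answers 72/180 = 40.0%. Difference −3.9 points. This is a ceiling: it takes every planned drop-out as having a CRF answer and no daily record.
- At an assumed 30% rate among 180 children with m = 9, expected counts give 51.3/(180 − 2.7) = 28.9% against 54/180 = 30.0%, or −1.1 points. With m = 2 they give 53.4/(180 − 0.6) = 29.8%, or −0.2 points.

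**Fever.** Step 1 does not apply, so both answers become missing and the SAP rate is Y/c = 61/153 = 39.9% whatever y is. With m = 27, using all answers would give 61/180 = 33.9% if y = 0 and 81/180 = 45.0% if y = 20. The shift can go either way.

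**Discontinuation events (4.2.2.5).** For an event of missing grade marked as having ended participation:

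| Table | Solicited | Unsolicited |
|---|---|---|
| Disposition | counted if the completion form gives an adverse event | same |
| Safety overview | counted through the completion form only | counted through the form or the event |
| SOC/PT | not counted | counted if within the time period |

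**The case against.** The strongest reply is that the situation may hardly arise. Protocol 8.3.2 has the investigator interview the parents, clarify incomplete entries and report information missing from the diary. Protocol 10.2.5 requires a grade for every AE. Table 1.1 asks for the whole visit to be completed when a child discontinues at a visit, and Protocol 7.2 expects withdrawal to be uncommon. A 'No' with an empty daily grid may simply be the normal record of a child without that reaction, and treating it as None is reasonable.

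Much of this stands and limits the size. It does not remove the gap. The footnotes to Protocol Tables 10.1 and 10.2 say that grades other than for erythema, swelling and fever are transcribed from the diary card, and the schedule collects that card only at Visit 2, although it lists solicited reactions at the day 9 call too. Step 1 itself anticipates presence answers without daily records.

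A reader might infer more than the documents support:

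- *That incomplete diaries can only lower the solicited rates.* This fails for fever, as shown above. It also fails for a child with no CRF answer, who is simply excluded. A partial diary with any graded day still counts as a reaction.
- *That lost or withdrawn toddlers are turned into non-reactors.* Step 1 needs a recorded 'No'. Loss to follow-up under Protocol 7.3 does not create one.
- *That 27 children are affected.* The 15% links enrolment to evaluable participants, whom Protocol 9.3.2 equates with the per-protocol set. A child excluded for, say, an out-of-window blood sample may have a full diary. SAP section 5 also says recruitment stopped short of 180.
- *That an ungraded 'Yes' becomes a non-event in an any-reaction row.* The SAP gives no derivation for such a row.

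**Conclusion.** The point holds for the eight non-fever solicited reactions. Followed as written, the SAP keeps recorded negatives and discards recorded positives among children with a CRF answer and no daily records, and it lowers those rates whenever at least one such 'Yes' exists and not every child reacts. No direction is claimed for fever or for children without a CRF answer.

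The size depends on a count that the documents do not give. Under the assumed rates it is about −0.2 points with two such children (30%), −1.1 with nine (30%) and −1.5 with ten (40%), with −3.9 at 40% as a ceiling. If no child has a 'Yes' without daily records, there is no effect.

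The 4.2.2.5 asymmetry is real but secondary. The child still appears in the disposition and overview tables when the completion form gives an adverse event; what can be lost is the named event in the SOC/PT table. The analyses are descriptive, so no test is affected. It remains a rule that can give a wrong percentage and is cheap to correct.

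**What to change.** In SAP 4.2.1.1.1, after step 1, add a rule for solicited reactions other than fever: when CRF presence is 'Yes' and all daily records are missing, set presence to Yes and maximum intensity to Missing. State in 4.2.1.1.3 that this overrides the derivation of presence from maximum intensity. Count the child in the numerator and denominator of the presence rows, show a missing-grade line in the intensity rows, and report for each reaction how many children have a CRF answer without daily records, split by Yes and No.

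Leave fever based on measured temperature. Without that exception the new rule would create the reverse error, because a fever 'No' would still be missing: on the ceiling counts, 72/(153 + 11) = 72/164 = 43.9% against 40.0%.

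In SAP 4.2.2.5, let both solicited branches (safety overview and SOC/PT) accept a missing grade, as the unsolicited branches do.

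The cost is a few sentences and a small change to the derivation program; step 1 already relies on the CRF presence field. The downside is that reported rates may rise slightly and the intensity tables gain a missing line.

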4.2.1.1.2 Maximum Intensity

Maximum overall intensity is derived from the daily intensities computed as described in Section 4.2.1.1.1 and is calculated as the maximum of the daily intensities over the period considered.

4.2.1.1.3 Presence

Presence is derived from the maximum overall intensity over the time period considered:

- None: No presence
- Grade 1, Grade 2, or Grade 3: Presence
- Missing or Unknown: Missing presence

Participants with at least one non-missing presence for a specific endpoint will be included in the analysis. Conversely, those without a non-missing presence will not be included in the analysis of the endpoint.

The time period is displayed as D1-D4, D5-D8, D9 and later.

4.2.1.1.4 Time of Onset

Time of onset is derived from the daily intensities computed as described in Section 4.2.1.1.1. It corresponds to the first day with intensity of Grade 1, Grade 2, or Grade 3.

Note: If a reaction is not continuous (i.e., reaction occurs over two separate periods of time intervened by at least one daily intensity Missing or None) then the time of onset is the first day of the first occurrence.

Time of onset period is displayed as, D1-D4, D5-D8.

4.2.1.1.5 Number of Days of Presence During the Solicited Period

Number of days of presence over the solicited period (D1-D8) considered is derived from the daily intensities computed as described in Section 4.2.1.1.1. It corresponds to the number of days with daily intensities of Grade 1, Grade 2, or Grade 3. Number of days of presence on the solicited period with a specified intensity may also be derived.

4.2.1.1.6 Overall Number of Days of Occurrence

If a reaction is ongoing at the end of the solicited period, then the overall number of days of presence is derived from the daily intensities and the end date of the reaction after the end of the solicited period. The overall number of days of presence is:

(End date - last vaccination date) + (number of days of presence within the solicited period) - length of the solicited period + 1

If the end date is missing or incomplete (contains missing data), the overall number of days of presence will be considered as Missing.

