	primed with 1 dose of another MCV4 vaccine	•	Antibody titers against meningococcal		
5)	during infancy		serogroups A, C, W, and Y		
5)	To describe the antibody responses to tetanus toxoid before and 1 month after a booster dose	•	Antibody titers $\geq 1:8$ and $\geq 1:128$		
	of MenQuadfi® in toddlers 12-23 months of age	•	≥ 4-fold rise from pre-vaccination to post-vaccination		
	who had been primed with at least 1 dose of		Vaccine seroresponse defined as follows:		
	another MCV4 vaccine during infancy		For a participant with a pre-vaccination titer		
	another fire v4 vaccine during infancy		< 1:8, a post-vaccination titer \ge 1:32		
			For a participant with a pre-vaccination titer		
			≥ 1:8, a post-vaccination titer at least 4-fold		
			greater that the pre-vaccination titer		
		3)	Same endpoints as described for endpoint #2		
		4)	Same endpoints as described for endpoint #2		
		5)	Antibody concentrations against tetanus toxoid		
			at D01 (baseline) and at D31 (+14 days) after		
			the administration of a booster dose of		
			MenQuadfi®		

Safety	Safety	
To describe the safety profile of a booster dose of MenQuadfi® administered to toddlers 12-23 months of age who had been primed with at least 1 dose of another MCV4 vaccine during infancy	 Presence of any unsolicited systemic adverse events (AEs) reported in the 30 minutes after vaccination. Presence of solicited (pre-listed in the participant's diary card [DC] and case report form [CRF]) injection site reactions up to 7 days after vaccination. Presence of solicited systemic reactions (pre-listed in the participant's DC and CRF) up to 7 days after vaccination. Presence of unsolicited AEs up to 30 days after vaccination. Presence of serious adverse events (SAEs) [including AESIs], throughout the trial from Visit 1 to 30 days after study vaccination. Depending on the items, the endpoints recorded or derived could include: Nature (Medical Dictionary for Regulatory Activities [MedDRA] preferred term), time of onset, duration/number of days of occurrence, intensity, relationship to the vaccine, whether the AE led to early termination from the study, outcome, and seriousness criterion 	

3 Statistical Considerations

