4.2.1.1.7 Ongoing

Ongoing is derived from the last daily intensity of the solicited period computed as described in Section 4.2.1.1.1 and the maximum intensity on the ongoing period. The investigator's ongoing flag is not used because the measurement would determine the ongoing status of the reaction.

- Ongoing: If the last daily intensity of the solicited period is at least Grade 1 and the maximum intensity on the ongoing period is at least Grade 1.
- Not ongoing: If the last daily intensity of the solicited period is None or the maximum intensity on the ongoing period is None.
- Missing: all other conditions (in this case, it is not included in the denominator of the ongoing analysis in safety tables).

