 - Else if the "Year of AE start date" > "Year of (last vaccination date + 30 days)", then this unsolicited AE will be categorized as "not within 30 days".

A few examples of missing time of onset with start date of AE partially missing:

First injection	Last injection	Start date of the AE	Injection date + 30	Will be analyzed "Within 30 days"?
date	date			· · · · · · · · · · · · · · · · · · ·
16Oct2023	16Oct2023	Missing	N/A	Y
16Oct2023	16Oct2023	Sep2023	N/A	N
16Oct2023	16Oct2023	Oct2023	15Nov2023	Y
16Oct2023	16Oct2023	Nov2023	15Nov2023	Y
16Oct2023	16Oct2023	Dec2023	15Nov2023	N
05Jan2023	05Jan2023	2022	N/A	N
16Oct2023	16Oct2023	2023	15Nov2023	Y
08Dec2023	08Dec2023	2024	07Jan2024	Y
16Oct2023	16Oct2023	2024	15Nov2023	N

Time of onset period is displayed as D1-D4, D5-D8, D9-D15, D16 or later, and Missing.

4.2.1.2.5 **Duration**

Duration is derived from the start and end dates of the unsolicited AE:

Duration = End date of unsolicited AE – start date of unsolicited AE + 1.

The duration is considered as missing only if one or both of the start and end dates of the unsolicited AE is missing or partially missing.

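### Events still open at last contact get a missing duration instead of a censored one, and reactions present on D8 with no later record leave the ongoing denominator

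*SAP*

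**What the plan says.** SAP Table 2.1 names "duration/number of days of occurrence" among the items that the safety endpoints could include. Three parts of the SAP govern it.

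- **Solicited reactions.** SAP 4.2.1.1.5 counts days of presence within D1 to D8 from the daily intensities and needs no end date: "It corresponds to the number of days with daily intensities of Grade 1, Grade 2, or Grade 3". An end date matters only for reactions that outlast that period: "If a reaction is ongoing at the end of the solicited period, then the overall number of days of presence is derived" (SAP 4.2.1.1.6). For these, "If the end date is missing or incomplete (contains missing data), the overall number of days of presence will be considered as Missing". SAP 3.4.5.1.4 adds: "Missing or partially missing end dates for ongoing solicited AEs will remain missing and not be imputed".
- **Unsolicited AEs.** SAP 3.4.5.1.4: "If either the start date or end date is missing or partially missing, the duration will be considered missing". SAP 4.2.1.2.5 repeats the rule.
- **Ongoing status of solicited reactions.** Under SAP 4.2.1.1.7, *Ongoing* needs both a D8 intensity and a later intensity of at least Grade 1. *Not ongoing* needs only one of the two to be None. Everything else is "Missing: all other conditions (in this case, it is not included in the denominator of the ongoing analysis in safety tables". The investigator's own ongoing flag is not used.

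Neither document says how an event unresolved at last contact appears in a duration table, or whether events with Missing duration are shown or left out.

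**The concern.** An event that has not resolved when the child is last seen has no end date, but its duration is not unknown: it is at least the time from onset to last contact. Setting it to Missing discards that lower bound. The chance of being open at last contact rises with the true length of the event, so the events set aside are on average the longer ones. A duration table restricted to the rest would lean short, and a categorical table would under-fill its longest categories.

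The ongoing table has a related weakness. A None on D8 settles the status by itself, whereas a Grade 1 or above on D8 needs a second record to count. When follow-up is absent, the reactions removed are therefore mostly those that might have continued.

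At stake is the description of how long reactions and AEs last, in an uncontrolled study with no comparator sharing the same distortion.

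**Working it through.** The documents give no duration figure to reproduce, so the check covers the SAP's formula first, then the direction and possible size of the effect.

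**1. The formula for overall days (SAP 4.2.1.1.6) is right.** It is (end date − vaccination date) + days within D1–D8 − 8 + 1.
- Present D1 to D10: 9 + 8 − 8 + 1 = 10 days.
- Present D8 to D10: 9 + 1 − 8 + 1 = 3 days.

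The issue is only what happens when there is no end date.

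**2. Who can be open at last contact.** Visit 2 falls on D31 to D45 (schedule of activities). Solicited reactions start by D8, so one still open on D31 has lasted at least 31 − 8 + 1 = 24 days. Unsolicited AEs count with onset up to D31 (SAP 4.2.1.2.4), so one starting late can be open after a day or two.

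**3. Hand illustration, unsolicited AEs.** Assumptions, not in the documents: onset uniform over D1–D31, durations L in equal thirds, every Visit 2 on day V, an event kept only if onset + L − 1 ≤ V, and Missing left out. Kept onset days out of 31 = min(31, V + 1 − L). Reported mean = Σ(L × kept) / Σ kept.

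| Visit 2 | Kept, L = 3/14/28 (true mean 15.0) | Dropped | Mean | Kept, L = 3/7/14 (true mean 8.0) | Dropped | Mean |
|---|---|---|---|---|---|---|
| D31 | 29, 18, 4 | 42/93 = 45% | 451/51 = 8.8 | 29, 25, 18 | 21/93 = 23% | 514/72 = 7.1 |
| D38 | 31, 25, 11 | 26/93 = 28% | 751/67 = 11.2 | 31, 31, 25 | 6/93 = 6% | 660/87 = 7.6 |
| D45 | 31, 31, 18 | 13/93 = 14% | 1031/80 = 12.9 | 31, 31, 31 | 0 | 744/93 = 8.0 |

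**4. Simulation with other shapes.** 400,000 events per scenario; durations geometric, or log-normal with log-SD 1; solicited onset mostly D1–D2; unsolicited onset uniform over D1–D31. These are again assumptions. Ranges run over the two shapes and, for solicited reactions, also over the two means and the three Visit 2 days.

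| Events (nominal mean) | Visit 2 | No end date | Mean too short by |
|---|---|---|---|
| Solicited, 3 to 5 days | D31, D38 or D45 | 0.0% to 1.1% | 0% to 8% |
| Unsolicited, 5 days | D31 | 12.9% to 14.2% | 15% to 23% |
| Unsolicited, 5 days | D45 | 0.6% to 1.7% | 2% to 10% |
| Unsolicited, 10 days | D31 | 27% to 28% | 34% to 38% |
| Unsolicited, 10 days | D45 | 6% to 7% | 15% to 24% |

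The mean was never too long. Open events were longer on average but not one by one: with Visit 2 on D31, about 11% to 20% of open unsolicited AEs were no longer than the overall median and were open only because they began late.

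**5. Ongoing share.** Suppose 15 of 100 reactions truly persist past D8, and 5 that were present on D8 have no later record. If a fraction q of those 5 persist, SAP 4.2.1.1.7 reports (15 − 5q)/95.
- q = 1: 10/95 = 10.5%.
- q = 0: 15/95 = 15.8%.
- Break-even: 15 − 5q = 0.15 × 95 = 14.25, so q = 0.15.

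The share is too low whenever the dropped reactions persist more often than reactions in general. That is expected, because all 5 were present on D8 while the other 95 include reactions already gone. Reactions with a missing D8 record and no later None also fall into Missing; this reasoning does not cover them.

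**The case against.** The case for leaving the SAP alone has several sound parts.

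- **Duration is a minor item.** It is an optional descriptor in a study without hypotheses. SAP Table 3.1 plans counts and percentages for safety, with no mean or median duration, so the means above illustrate a statistic that is not planned.
- **Exclusion is not stated.** Where the SAP leaves missing values out it says so (4.2.1.1.3, 4.2.1.1.7), and for unsolicited time of onset it displays a Missing category. For duration it is silent. A reader might infer that open events vanish from the report; the documents do not say that.
- **Long events stay visible elsewhere**: in presence by period (including D9 and later), days within D1–D8, ongoing status, and outcome. None of these gives a length beyond D8, however.
- **Follow-up closes part of the gap.** Protocol 8.3.3 follows serious, related, discontinuation-causing and special-interest AEs to resolution or stabilization during the study, and solicited reactions are related by convention. Follow-up beyond the study's end is mentioned only for related SAEs. The remainder is mainly non-serious unsolicited AEs judged unrelated.
- **An absent end date is not proof of an open event.** It may simply be unrecorded or partial.

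These points limit the importance. They do not supply a rule for events known to be unresolved.

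**Conclusion.** The point holds as a minor one. The SAP treats right-censored durations as missing, for solicited reactions ongoing after D8 and for unsolicited AEs. Any summary that omits Missing would tend to be too short. The effect falls mainly on late-onset unsolicited AEs, and is nil to small for solicited reactions lasting a few days. The ongoing share is expected to be too low.

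The size cannot be known from the documents. It depends on the duration distribution and on where Visit 2 falls between D31 and D45. Three stronger readings are tempting but unsupported:

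- That every reaction without an end date loses its duration. Reactions confined to D1–D8 need no end date.
- That the error always favours the vaccine. The 15/95 case shows that the ongoing share can come out too high.
- That close to half of durations are lost. The 45% needs one third of AEs to last 28 days and every Visit 2 on D31; the 3/7/14-day mix shows no loss at D45.

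**What to change.** In SAP 3.4.5.1.4, 4.2.1.1.6 and 4.2.1.2.5, state that in any duration table an event unresolved at last contact stays in the denominator and appears in its own row as 'ongoing, at least k days', with counts. Count k to Visit 2 or termination: last contact − start date + 1 for an unsolicited AE, and the existing formula with last contact in place of the end date for a solicited reaction. Keep end dates that are simply unrecorded in a separate Missing row, together with AEs whose start date is incomplete. A Kaplan-Meier median is optional.

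In SAP 4.2.1.1.7, show a D8 intensity of Grade 1 or above with no later record as its own row, 'present at last record', inside the denominator. This avoids counting it either as ongoing or as resolved.

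Outcome, last-visit and termination dates are already available (SAP 4.2.2.3 and 4.2.5.3). The cost is a few sentences, a small programming change and slightly less favourable figures.
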